7.2.1 NS metric

The NS metric is a continuous indicator on a 000-999 scale, with the last digit representing number of active opioid prescriptions (those with ≥ 9 prescriptions coded as 9) and the first two numbers representing a composite risk score. Higher scores indicate increased risk for adverse opioid-related outcomes (e.g., overdose). The first two digits of the score are based on deterministic calculations^{3,4} and use well-known indicators associated with opioid-related adverse events.⁴⁹⁻⁵² These calculations are produced through the following steps:

- 1) For a given patient, raw indicators of five risk factors are extracted from PDMP data: (a) morphine milligram equivalents (MME) dispensed, (b) lorazepam milligram equivalents (LME) dispensed, (c) overlapping prescription days, (d) number of prescribers, and (e) numbers of pharmacies.
- 2) Each raw indicator is converted to a scaled value between 0 and 99 (based on percentiles from a large PDMP reference population), for four time periods: (a) past 2 months, (b) past 6 months, (c) past 12 months, and (d) past 24 months. Therefore, each patient is assigned 20 scaled percentile values. These scaled values weigh the contribution of recent values more heavily than values further in the past; for example, having 6 unique prescribers over the past 2 months has a greater scaled percentile score (i.e., 85) than having 6 unique prescribers over the past 2 years (i.e., 30).
- 3) Scaled values for each of the five indicators are averaged across their four respective time periods.
- 4) A weighted sum of the five averaged values is calculated: MME is given a weight of 3; overlapping medication days is given a weight of 2; and LME, number of prescribers, number of pharmacies are each given a weight of 1. This sum is divided by 8 to produce a weighted average, yielding a two-digit composite risk score; these are the first two digits of the NS metric.
- 5) The total number of active opioid prescriptions is appended to the two-digit composite risk score, to form the final three-digit NS metric.

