The study will be powered to the least prevalent but most severe condition among potential patients. Based on the allocation ratio of the national rate of prescription opioid use disorder (POUD) among those prescribed opioid medications in the last year, the prevalence of Poud is 2.1%. A sample of approximately 1,523 (32 positive group) achieves 97.68% power to detect a difference of 0.2 between the area under the ROC curve (AUC) under the null hypothesis of 0.5 and the alternative hypothesis of 0.7 using a two-sided z-test at a significance level of 0.050.

The Completer Population (both training and testing set) will be used to assess the overall discrimination ability of NS metric.

*To determine cut-point threshold values for NS total score:*

The objective is to select the optimal cut-points threshold for NS metric to define low, moderate and high risk groups. We will use a hybrid framework where we can make use of the data driven methods to support the clinician's final decision making. Only the training data set will be used in this portion of analysis.

In the first step, the solution space (a subset of optimum choices of cut-point threshold values) will be identified with the following grid search approach: for each pair of risk groups, for example, low risk vs moderate risk, calculate the following performance measurements for each possible cut-point threshold value:

- Sensitivity (SE)

$$SE = \frac{\text{True Positive Rate}}{\text{True Positive Rate} + \text{False Negative Rate}}$$

- Specificity (SP)

$$SP = \frac{\text{True Negative Rate}}{\text{True Negative Rate} + \text{False Positive Rate}}$$

- Positive Predictive Value (PPV): probability that the risk level is present (based on WHO ASSIST) when the result with NS metric is positive.
- Negative Predictive Value (NPV): probability that the risk level is not present (based on WHO ASSIST) when the test result with NS metric is negative.
- Youden's index:

$$\text{Youden's Index} = SE + SP - 1$$

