Youden's index, a metric that summarizes both false positive and false negative misclassification rates with equal weights, will be used as primary evaluation criteria to compare classification performance across scenarios with different cut-points threshold values. A solution space, i.e. a set of cut-point threshold values with highest Youden's Index, will be selected. For example, the selected solution space of low risk vs moderate risk cut-point threshold is 10-30, which gives the highest 10% Youden's Index among all possible choices (0-999). See **Table 2** as an example of grid search result:

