### **Exploratory Statistical Aim 3: To validate definition of NS metric.**

In this section, we will validate the definition of NS metric and test if the third digit of NS metric (number of opioid prescription) is informative. We will examine an alternative definition of NS metric, named as NS metric v2, which consists of only the first two numbers of original NS metric, which ranges 00-99. Descriptive analyses will be conducted and correlation between NS metric and NS metric v2 will be examined with Spearman Correlation Coefficients. We will repeat the planned training/validation analyses in the primary analysis and compare the discriminative ability of NS metric v2 vs. NS metric. We expect the predictive power of NS metric v2 is lower than that of NS metric, which implies the 3rd digit in NS metric original definition is predictive. We will also repeat the training/validation analysis within each subgroup of patients with same numbers of opioid prescriptions. The overall discriminate ability for NS metric 2, described by average misclassification rate across subgroups, will be compared with primary analyses results. It is expected that the prediction accuracy is comparable, which implies the “opioid prescription number” information is well represented by the third digit of original NS metric definition.

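### SAP Exploratory Aim 3 draws two conclusions about the third digit from point comparisons: the first needs a paired confidence interval, and the second does not follow

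*SAP*

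**What the plan says.** SAP 3.5, Exploratory Statistical Aim 3, sets out to "test if the third digit of NS metric (number of opioid prescription) is informative". It defines v2 as the first two digits of the NS metric, repeats the training and validation analyses with it, and attaches a conclusion to each of two expected results.

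- First comparison, v2 against NS: "We expect the predictive power of NS metric v2 is lower than that of NS metric, which implies the 3rd digit" is predictive.
- Second comparison: the analyses are rerun among patients with the same prescription count. The result, "described by average misclassification rate across subgroups, will be compared with primary analyses results". Then: "It is expected that the prediction accuracy is comparable, which implies the" count is well carried by the third digit.

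The aim names no difference statistic, paired test, confidence interval or margin. It does not define comparable, or say how subgroups are weighted in the average. Protocol 9.4 sets a general two-sided 5% level but no method for comparing two scores in the same patients. The 95% intervals in Exploratory Aim 1 cover Spearman, Gamma and Kendall coefficients, not a difference between AUCs. The output list in SAP Appendix 1 has no entry for Exploratory Aim 3.

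Protocol 7.2.1 gives the structure of the score: "The total number of active opioid prescriptions is appended to the two-digit composite risk score, to form the final three-digit NS metric".

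**The concern.** The aim's title says it validates the definition of the NS metric, and the wording of both conclusions is fixed in advance. Read from point estimates, the first could credit a digit that carries no information. A small gap between NS and v2 could also be taken to mean that the prescription count adds little, when the way the score is built keeps that gap small whatever the count is worth. The second could certify that the count is well represented when most of its information has been lost.

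**Working it through.** **1. The plan's own figure.** Exploratory Aim 3 gives none. The only AUC calculation in the SAP is 97.68% power for one AUC, 0.7 against 0.5, with 32 positives in 1,523 (two-sided 5%). With the Hanley–McNeil variance and 32 against 1,491:

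- SE at 0.5 = √(127/47,712) = 0.0516; SE at 0.7 = 0.0523.
- Power = Φ((0.2 − 1.96 × 0.0516)/0.0523) = Φ(1.89) = 0.971. The binormal variance gives 0.977.

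The figure is reproduced, but it concerns one AUC against 0.5, not NS against v2.

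**2. What the third digit can change.** From Protocol 7.2.1, NS = 10 × composite + count, with count 0 to 9. A composite difference of 1 adds 10 and outweighs any count difference, so only patients with equal composites are reordered. Let p_k and q_k be the shares of positives and negatives with composite k, and A_k the AUC of the count among them. Then

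AUC(NS) − AUC(v2) = Σ p_k q_k (A_k − 0.5),

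which cannot exceed half the tied-pair share, ½ Σ p_k q_k. For a composite uniform on 00–99 that is ½ × 0.01 = 0.005. For a roughly normal composite (mean 35, SD 18) the tied share was 0.0139, so the limit is about 0.007. More concentrated assumed distributions gave up to 0.042.

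**3. First comparison.** If the count is uninformative, A_k scatters around 0.5 and the sign of the difference is chance. Simulations used N = 1,523, the SAP's 17.1% and 2.1% prevalences, several assumed composite distributions, and count–composite correlation 0 or 0.5.

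- v2 had the lower AUC in 44–55% of studies.
- A paired DeLong 95% interval excluded zero in 1.7–6.6%.

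The paired interval is also sharp. Under the mean-35, SD-18 composite its half-width was 0.0013–0.0015 (high against the rest) and 0.0006–0.0007 (moderate against low). Treating the AUCs as independent would give 1.96 × √2 × 0.0523 = 0.145. With a modest or strong count effect the mean gain was only 0.0018–0.0063, yet the interval lay above zero in 94–100% of studies.

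The size of the gap says little about the count. At log-odds 0.5 per prescription, 17.1% positives and correlation 0, NS minus v2 was 0.003–0.011. The count as a separate model term added about 0.035 to 0.08, depending on its assumed distribution.

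**4. Second comparison.** Within a count subgroup the digit is constant, so NS and v2 rank patients identically. Mean test-set misclassification over 400 studies per row (levels 82.9/15.0/2.1%, 1:1 split, maximum-Youden cut-points, subgroups weighted by size):

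| Correlation | Count effect | Within-count | Primary NS | Difference |
|---|---|---|---|---|
| 0 | none | 0.389 | 0.392 | −0.003 |
| 0 | modest | 0.387 | 0.406 | −0.019 |
| 0 | strong | 0.413 | 0.422 | −0.010 |
| 0.5 | none | 0.405 | 0.397 | +0.008 |
| 0.5 | modest | 0.409 | 0.359 | +0.050 |
| 0.5 | strong | 0.487 | 0.341 | +0.147 |

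In the third row the count alone had AUC 0.767 against 0.700 for NS (moderate against low). The appended digit therefore represents the count poorly, yet the error rates differ by only 0.01.

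Other assumed distributions (binary outcome, 17.1% positives, log-odds 0.5, correlation 0) gave differences of −0.008 to −0.001. There the joint composite-plus-count model exceeded NS by 0.070–0.081 in AUC, or by about 0.03 when every patient was given at least one prescription.

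Across simulations the SD of one study's difference was about 0.06 to 0.12. In the tabulated runs an average of 3.2 to 6.5 count subgroups per study had no estimable cut-points, because only about 32/2 = 16 high-risk patients fall in the training half.

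**The case against.** The strongest reply is that the aim is the last of three exploratory ones, that it states expectations rather than decision rules, and that the word test together with Protocol 9.4 implies some formal comparison. It is right that nothing downstream depends on the aim, which keeps the severity low. But no test is named, and both sentences attach a conclusion to a bare result.

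A second reply is that comparable accuracy together with a large loss appeared only at zero correlation, whereas the composite draws on related dispensing data ("raw indicators of five risk factors are extracted from PDMP data: (a) morphine milligram equivalents (MME) dispensed"), so some correlation is likely. This stands as a limit on how often the second conclusion would mislead. It does not make the conclusion valid: an irrelevant count also gave small differences, with nothing to represent, and one study's difference is noisy enough to look comparable or not by chance.

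Three stronger readings are tempting and are not supported.

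- **The comparison is bound to favour NS.** Every v2 cut-point is also an NS cut-point, so v2 cannot beat NS on Youden's index in the training set. But the SAP gives Youden's index a different job: it "will be used as primary evaluation criteria to compare classification performance across scenarios with different cut-points threshold values". Discrimination is measured by AUC, and "The Completer Population (both training and testing set) will be used to assess the overall discrimination ability of NS metric". Training-set Youden is not the planned comparison of the two scores.
- **The within-count result reflects only the correlation between count and composite.** At correlation 0.5 it rose with the count effect, from +0.008 to +0.147, so both matter.
- **Appending costs 0.08 in AUC.** That figure came from a count distribution with about 22% of patients at zero active prescriptions, although eligibility requires at least one dispensed opioid. With at least one prescription each, it fell to about 0.03. The documents give no distribution that would settle it.

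**Conclusion.** The point holds in two parts. The first conclusion is sound in principle, but only if a paired interval for AUC(NS) minus AUC(v2) lies above zero; the bare sign is close to a coin toss when the count is uninformative. The second conclusion does not follow from its result, and defining a margin for comparable would not rescue it, because opposite situations gave differences near zero.

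The tie-only action of the digit and its constancy within subgroups follow from the documents alone. Every simulated size depends on assumed distributions of composite and count, an assumed correlation, and a pure maximum-Youden cut-point in place of the clinician's choice.

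Severity is low. A reader might infer that the cut-points or the Aim 1 and Aim 2 conclusions are in doubt; they are not, since none of them uses this aim.

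**What to change.** - Report AUC(NS) minus AUC(v2) in the full Completer Population, as SAP 3.5 already does for the AUC, with a paired 95% interval (DeLong or bootstrap). Call the digit predictive only if the interval lies above zero, and state that a small difference does not show that the count adds little.
- Delete the second conclusion. Keep any within-count reruns as descriptive only.
- To assess whether appending captures the count, fit an ordinal logistic model of ASSIST level on the two-digit composite and the number of active prescriptions as separate terms. Give a likelihood-ratio test for the count. Compare the joint model's AUC (optimism-corrected or in the test set) with that of NS, using a paired interval.

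The cost is a few lines of SAP text and one extra exploratory model. Both components are already in the score, and Aim 2 already uses an ordinal logistic model. There are two drawbacks. The joint model asks about the count's own weight rather than the digit as appended. Power is also low for the rare high-risk level: with 2.1% positives and log-odds 0.2 per prescription, the paired interval excluded zero in 9–23% of simulated studies, and a likelihood-ratio test from a binary logistic model detected the count in 25–33%. An interval that includes zero would therefore not show that the digit is uninformative.

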**Table 2: Grid search result for threshold value of moderate vs high risks**

Possible Threshold values for high risk vs moderate risk	Youden's Index	SE	SP	PPV	NPV	Rank of Youden's Index	Flag for solution space
0	XXX	XXX	XXX	XXX	XXX		
...							
511	XXX	XXX	XXX	XXX	XXX	10/1000	Yes
512	XXX	XXX	XXX	XXX	XXX	100/1000	Yes
513	XXX	XXX	XXX	XXX	XXX	200/1000	No
...							
999	XXX	XXX	XXX	XXX	XXX		

In the second step, the final optimal cut-points threshold values will be selected from the solution space, with clinical justification such that the balance between sensitivity and specificity is achieved. For example, a cut-off point of 20 is selected for low risk vs moderate risk group based upon clinician's justification. This framework will integrate clinical knowledge into purely data-driven techniques.

Assuming the acceptable SE and SP are 0.8 for both cutoffs (low vs moderate/high and low/moderate vs high), with a sample size of 750 patients in the training data set, the width of 95% confidence intervals of SE and SP estimations are 0.026 and 0.056 for the classification cutoffs that predict low risk vs moderate/high (prevalence 82.9% vs 17.1%). For predicting low/moderate risk vs high risk (prevalence 2.1% vs 97.9%), the width of confidence intervals for SE and SP are 0.143 and 0.024, respectively. The narrow confidence intervals imply relatively high precision for the SE and SP estimations, which will be used to support clinicians' decision making.

The final selected cut-points threshold values will be validated with an independent testing data set in Aim 2.

**Statistical Aim 2 – To validate discriminative ability of NS metric (with the established risk levels of low, moderate, and high) as a clinical measure to evaluate opioid use risk level.**

The second primary aim of the project is to evaluate the concurrent validity of the NS metric with the established risk levels of low, moderate, and high. Classification accuracy will be evaluated with an independent testing data set, and WHO ASSIST will be used as the gold standard to define actual risk levels for patients. The agreement level of risk groups defined by NS metric and WHO ASSIST will be descriptively summarized with a confusion matrix, see **Table 3**. Each row of the matrix represents the instances and percentages in a predicted risk level while each column represents the instances in an actual risk level.

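### The subgroup step of Exploratory Aim 3 describes discrimination by an average error rate on which a no-information rule (17.1% wrong) beats the SAP's acceptable classifier (23–32% wrong), and sparse count strata add to the problem

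*SAP*

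**What the plan says.** Exploratory Statistical Aim 3 (SAP 3.5) has two parts. The first repeats the primary analyses on the whole sample with the third digit removed, in order to "compare the discriminative ability of NS metric v2 vs. NS metric". The second is the subject here: "We will also repeat the training/validation analysis within each subgroup of patients with same numbers of opioid prescriptions". It continues: "The overall discriminate ability for NS metric 2, described by average misclassification rate across subgroups, will be compared with primary analyses results". The stated prediction is: "It is expected that the prediction accuracy is comparable". That outcome would be taken to show that the third digit carries the count information well. This part gives no formula for the rate, no weights, no reference rule and no chance-corrected measure.

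The planning figures are under Statistical Aim 1. The target performance is given as "Assuming the acceptable SE and SP are 0.8 for both cutoffs (low vs moderate/high and low/moderate vs high". The prevalences are given for "the classification cutoffs that predict low risk vs moderate/high (prevalence 82.9% vs 17.1" percent, with 2.1% high risk. Cut-points are chosen by Youden's index. The primary analyses report AUC, kappa and Spearman correlation.

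**The concern.** A raw error rate weights each risk class by how common it is. When about five patients in six are low risk, it mostly records how often low-risk patients are flagged, so a rule that flags nobody can look best. Cut-points would thus be chosen on a criterion that ignores prevalence and judged on one dominated by it.

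Splitting by count adds two difficulties. If strata are averaged equally, small ones count as much as large ones. A stratum with no high-risk training patient has no sensitivity for the upper cut-point, so Youden's index cannot be computed there, and the SAP gives no fallback. Because the SAP fixes the interpretation of comparable accuracy in advance, a figure shaped by prevalence and sparse strata could be reported as evidence about how the score is built.

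**Working it through.** **Plan's own figure.** The documents state no misclassification rate. The nearest figure on the same prevalence is the power for AUC 0.7 against 0.5 with N = 1,523 and 32 positives (0.021 × 1,523 = 32), two-sided 0.05, stated as 97.68%. Using Φ((0.2 − 1.96·SE₀)/SE₁), the Obuchowski binormal variance gives 97.73% and the Hanley–McNeil variance 97.06%. The planning inputs reproduce.

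**Inputs (SAP 3.5, Statistical Aim 1).** Low 0.829; high 0.021; moderate 0.171 − 0.021 = 0.150; SE = SP = 0.80 at both cut-offs.

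**Everyone labelled low.** Error = 1 − 0.829 = 17.1%; kappa = 0.

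**Acceptable classifier, three levels.**
- Low: 20% wrong, contributing 0.829 × 0.20 = 0.1658.
- High: 20% wrong, contributing 0.021 × 0.20 = 0.0042.
- Moderate, minimum. At the lower cut, missed patients total 0.20 × 0.171 = 0.0342. At most 0.0042 of these are high risk, so at least 0.030 are moderate. At the upper cut, false positives total 0.20 × 0.979 = 0.1958. At most 0.1658 of these are low risk, so at least 0.030 are moderate. The minimum is 0.060.
- Moderate, maximum: all wrong, 0.150.
- Total: 0.1658 + 0.0042 + 0.060 = **23.0%**, up to 0.1658 + 0.0042 + 0.150 = **32.0%**. A linear program over the four constraints gives the same limits. Kappa is about 0.40 to 0.43 in the 23.0% configurations.

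**Break-even.** The minimum error is (1 − s)(0.829 + 2 × 0.150 + 0.021) = 1.15(1 − s). Setting this to 0.171 gives s = 0.851. At s = 0.90 the error is 11.5%, below the all-low rule.

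**Weighting.** With size weights, 17.1% and the 23.0% minimum hold however prevalence varies over strata, provided 0.80 holds in each. With a plain average and a constant moderate-to-high ratio (assumption), the minimum error is 0.20 + 0.20 × q × 0.150/0.171, where q is the mean moderate/high share. All-low stays ahead while q is below 0.243.

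**A stratum with no upper cut-point.** Keep 0.80 at the lower cut for each class and never predict high: 0.1658 + 0.150 × 0.20 + 0.021 = 21.7%. This is below the 23.0% minimum, although no high-risk patient is ever identified as high. A plain average gives such strata full weight.

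**Sparsity.** 32/2 = 16 high-risk patients per half. Spread evenly and at random (assumption):

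| Count strata | High-risk per stratum per half | Chance a given stratum has none, (1 − 1/k)¹⁶ | Chance at least one has none |
|---|---|---|---|
| 10 | 1.6 | 19% | 93% |
| 6 | 2.7 | 5% | 30% |
| 4 | 4.0 | 1% | 4% |

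**Simulation** (normal scores, count unrelated to risk, Youden cut-points, assumed count distributions). With size weights, stratifying moved the error by about 1 to 2 points on average. With a plain average over a skewed ten-value spread it fell from 0.44 to 0.36. The share of strata without a high-risk training patient ran from about 1% (four equal strata) to 55% (the skewed spread).

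**The case against.** *The rate is undefined.* In describing Youden's index the SAP uses misclassification rates in a class-specific sense. As an equal-weight mean of class errors the order reverses: all-low (0 + 1 + 1)/3 = 66.7%, against (0.2 + 0.4 + 0.2)/3 = 26.7%. This is a fair point, but the sentence that follows speaks of prediction accuracy, which fits the ordinary share of patients misclassified. The definition is needed either way.

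*The all-low rule is not a candidate.* Correct: Youden's index gives it 0. A reader might infer that the planned analysis would drift towards flagging nobody. The documents do not support that, and simulation does not show it: with size weights the share flagged was 0.31–0.43 stratified and 0.31–0.42 in the primary analysis. The all-low figure exposes a weakness of the measure. It does not predict what the fitted rules will do.

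*The number of empty strata is unknown.* Also correct. A reader might infer that the step cannot be run at all. With a few well-filled counts it can.

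*The step is minor.* It belongs to the third exploratory aim, Appendix 1 lists no table for it, and whether the third digit is predictive is addressed by the whole-sample comparison. This stands and sets the weight of the point.

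**Conclusion.** The point holds for the subgroup step only. At the planning prevalences, the error rate ranks a rule with no information (17.1%) ahead of a classifier the SAP would accept (23.0% to 32.0%), up to SE = SP of about 0.851. The 23% is a minimum at 0.80, not a floor for better classifiers. The result rests on the SAP's prevalences and on reading the rate as the share of patients misclassified.

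The artificial fall under a plain average, and the strata without an upper cut-point, depend on a count distribution the documents do not give, so they are ranges under assumption. Size weighting largely removes the first but not the second.

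No primary or secondary conclusion depends on this step. It is worth considering, not essential.

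**What to change.** Amend the second part of Exploratory Aim 3 as follows.

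1. Merge sparse prescription counts into a few adjacent groups by one rule fixed before analysis, stated as a minimum number of high-risk training patients per group. With about 16 available, a minimum of four allows at most 16/4 = 4 groups.
2. Keep the training/testing split of the primary analysis.
3. Pool the test-set predictions of the group-specific NS v2 classifiers into one 3×3 confusion matrix. Pooling weights groups by size automatically.
4. Compare its kappa, and its sensitivity and specificity at both cut-offs, with those of the primary NS classifier on the same test patients, with a paired bootstrap confidence interval.
5. If the misclassification rate is kept, define it and print it beside the all-low reference (17.1% at the planning prevalences).

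A count-stratified AUC would avoid cut-points but would not answer the question. Within one count NS is ten times NS v2 plus a constant, so both rank patients identically, and the stratified and crude AUCs cover different pairs of patients.

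The cost is somewhat coarser count groups, a short SAP edit and a little more code. No new data are needed.
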